## 14.1.4 Specification of the Model

For valid inference on the primary efficacy parameter, the evolution of  $FEV_1$  in both treatment groups should be modeled as a flexible function in time, without unnecessarily strong assumptions.

Therefore, time will be modeled assuming that the time evolution of  $FEV_1$  is a smooth function of time. Cubic splines will be used with a large enough number of parameters to minimize the risk of misspecification. We will choose one knot at 182 days, i.e., halfway between the first (day 28) and

the last scheduled measurement (337 days). So, it is assumed that the mean of FEV1 is a third-degree polynomial at each of the two intervals, smoothly connected, equal at day 182 with equal first and second derivative. Thus, 4 parameters per group are used to model time. In total, as many as 12 parameters in the model will involve time, ensuring robust estimation of the time evolution of FEV1. Denoting the covariates associated with the splines by S1=t, S2=t, S3=t and S4=max(t-182,0), the treatment group by T (0=SoC; 1=L-CsA plus SoC), the day of the measurement by t and the baseline FEV1 by X, the fixed part of the model will contain the following covariates:

The Kenward-Roger adjustment will be used for the denominator degrees of freedom needed for hypothesis tests and confidence intervals.

The other covariates are:

- Age (< 55 versus ≥ 55 years);

- Region (North America versus all other countries together);
- Use of azithromycin at randomization.

In the unlikely case of collinearity, covariates will be dropped in the above order, starting with the last.

The random part of the LMM will be selected by comparing the Akaike Information Criterion (AIC) of three models:

- model with random intercept and random time;
- model with random intercept, random time and random squared time;
- model with random intercept, random time, random squared time, and random cubic time.

The model with the lowest AIC will be adopted for the primary analysis.

The core excerpt of cole code for the primary analysis is reported in section 17.1.

## 14.1.5 Specification of the Covariance Model

The model for the mean uses the actual times of the visits as a continuous variable instead of the scheduled visit times. Therefore, the covariance model will also use the actual visit times, using random effects. For valid inference, the model for the covariance should be correctly specified. Thus, the preference will be for models with relatively many parameters in order to ensure robust estimation of the covariance, though this may lead to a loss of efficiency.

Therefore a model will be specified with four per patient random effects: intercept, t,  $t^2$ ,  $t^3$ , with an unstructured covariance matrix. This covariance model contains 11 parameters, ensuring sufficient robustness. In case the model does not converge, or the covariance matrix is not positive definite, we will drop terms from the highest order random effect.

Final Version 5.0 Page 42 of 76

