#### 8.3.1.3 Linear Mixed Model

A linear mixed model (LMM) for repeated measurements, similar to the analysis of the primary endpoint (section 14.1) was performed to model FEV1 measurements for each complete dataset. Since the IA was blinded, the treatment group, and the interactions of time splines by treatment were excluded from the model.

The model included change in  $FEV_1$  between baseline and subsequent visits as the dependent variable, and contain the following covariates (except from the intercept):

- Time splines:  $S_1=t$ ,  $S_2=t^2$ ,  $S_3=t^3$  and  $S_4=max(t-182,0)^3$  where t is the study day of the measurement and  $S_4=(t-182)^3$  if t>182 and 0 otherwise;
- base FEV1: Baseline FEV1;
- base\_FEV1\*S1,..., base\_FEV1\*S4: The interactions of time splines with the baseline FEV1;
- region: North America versus all other countries together;
- age group: age ( $< 55 \text{ versus} \ge 55 \text{ years}$ ).

In case the model did not converge, or the covariance matrix was not positive definite, consideration was taken to drop from the model the highest order random effect.

The adjusted mean change from baseline at Week 48 derived from the LMM was adjusted at the mean baseline FEV1 for all patients who were observed to complete the study or discontinued, not the mean of the covariates over all observations.

Final Version 5.0 Page 21 of 76

Results from each complete dataset was combined using Rubin's rule to provide the least square means (LSMs) for change at Week 48 from baseline as well as the standard error of the LSM. Let seall denote the estimated standard error of the mean change from baseline of FEV1 at Week 48.

The median of squared standard error over all complete datasets can be written as:

$$se_{all.median}^2 = v^2/(n_{complete} + w n_{drop-out})$$
,

where  $n_{complete}$  and  $n_{drop-out}$  denote the number of completer patients (i.e., having a 48 weeks measurement) and the number of patients who dropped-out, respectively, and w is the average weight of the drop-outs. The weight of the completer patients is by definition 1, and w (<1) quantifies the average contribution of the drop-outs to the estimation of the mean change from baseline of FEV1 at Week 48. The variance v2 is the residual variance of the change from baseline of FEV1 at Week 48 after adjustment for the covariates.

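### With time in raw days, the unit can decide which random effects the primary mixed model keeps; the SAP should define t as study day/336 before its drop rule and AIC comparison apply.

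*SAP*

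**What the plan says.** SAP 14.1.4 builds the spline from t, t², t³ and a truncated cubic. It denotes "the day of the measurement by t and the baseline" FEV1 by X, and it sets the knot in days: "We will choose one knot at 182 days, i.e., halfway between the first (day 28) and" the last scheduled measurement at day 337. The interim model in SAP 8.3.1.3 uses the same basis, "where t is the study day of the measurement".

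For the random part, SAP 14.1.4 compares three candidates by AIC and adopts the lowest. The richest is the "model with random intercept, random time, random squared time, and random cubic time". SAP 14.1.5 states that "the covariance model will also use the actual visit times, using random effects", and continues: "Therefore a model will be specified with four per patient random effects: intercept, t", t² and t³, with an unstructured matrix. It adds: "This covariance model contains 11 parameters, ensuring sufficient robustness". The fallback is: "In case the model does not converge, or the covariance matrix is not positive definite, we will drop terms from the highest order random effect".

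The readable text gives no centring or rescaling of t, no starting values, no tolerance and no step to try before a term is dropped. It does not say how a failed fit enters the AIC comparison. The program in SAP 17.1 and the content of Table 8 are blacked out.

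**The concern.** With t running to 337, t³ reaches about 3.8e7, while the intercept column stays at 1. Columns and variances that differ by so many orders of magnitude can defeat an optimiser, or fail a positive-definiteness tolerance, even when the data support the model. The fallback would then remove a random effect for a numerical reason. An AIC taken from a fit that stopped short of its maximum would also rank the candidates wrongly.

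At stake is the covariance model of the primary analysis. It sets the weight of incomplete patients and the Week 48 standard error. SAP 14.1.5 says that it prefers a richly parametrised covariance for valid inference, and that is the model most exposed. The same mixed model is refitted on the 200 imputed datasets of SAP 14.2.1 and in every tipping-point scenario of 14.2.2.

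**Working it through.** **Inputs from the SAP.** Nominal days for V2 to V9: 29, 57, 85, 113, 169, 225, 281, 337 (9.4, Table 2). Random effects 1, t, t², t³ (14.1.5). FEV1 in litres (7.3). 169 patients randomised (8.2).

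**Assumed, not in the documents.** Simulated data used random-effect SDs of 0.12, 0.45, 0.6 and 0.35 L on the t/336 scale, residual SD 0.08 L and about 15% of visits missing. Some runs also set 6% of patients to FEV1 = 0 after death or re-transplantation.

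**1. The plan's own counts reproduce.** Covariance parameters: 4 × 5/2 + 1 = 11. Parameters involving time: 4 + 4 + 4 = 12.

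**2. Conditioning of Z = [1, t, t², t³] at the nominal days.** The double-precision limit is 1/eps = 4.5e15.

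| Time unit | cond(Z) | cond(Z'Z) | Numerical rank of Z'Z |
|---|---|---|---|
| days | 8.2e7 | 6.8e15 | 3 of 4 |
| t/336 | 1.3e2 | 1.7e4 | 4 of 4 |
| (t − 183)/154 | 7.2 | 52 | 4 of 4 |

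Z itself has rank 4 in days. For the quadratic random part in days, cond(Z'Z) is 2.8e10, well inside the limit. With columns normalised, cond(Z'Z) is 9.3e3 in any uncentred unit, so the cause is scale and not collinearity.

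**3. Variance of the cubic effect in days.** For an SD of s litres at Week 48 it is (s/336³)², with 336³ = 3.79e7. For s = 0.05 this gives 1.7e-18, and for s = 0.5 it gives 1.7e-16. Beside an assumed intercept variance of 0.01 to 0.04, the condition number of the random-effects covariance matrix is 2e14 to 6e15 in days and 5 to 16 in t/336. A numerical tolerance can therefore reject a valid matrix.

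**4. The model does not depend on the unit.** The spline powers sum to 1 + 2 + 3 + 3 = 9 and enter three times (main effect, by treatment, by baseline). The REML log-likelihood should therefore shift by 27 × ln(336) = 157.062. Direct evaluation gave 157.0620. All three candidates share the fixed part, so the constant cancels in the AIC comparison.

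**5. The unit alone can change the outcome of a fit.** With the same data, a general-purpose REML optimiser and default starting values, the cubic random model was reported as converged in 0 of 6 simulated trials in days, and in 6 of 6 in t/336. A convergence flag is not full protection. In one trial the quadratic model in days was flagged as converged at log-likelihood −1134.68 with a Week 48 SE of 335 L. The t/336 fit gave 694.43 and 0.0761 L, so the value in days should have been 694.43 − 157.06 = 537.37.

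**6. What a change of random part does.** All fits here are in t/336.
- Six trials without zero imputation: linear versus cubic made the SE 7 to 9% smaller (for example 0.0791/0.0871 − 1 = −9%). A second set of simulated trials gave about 8 to 11%.
- Same six trials, quadratic versus cubic: effect moved by at most about 0.003 L, SE by under 2%.
- Six trials with the assumed 6% set to zero: among the four in which the quadratic model converged, quadratic versus cubic moved the effect by up to 0.02 L and the SE by about 1 to 22%. Linear versus cubic moved the SE from −12% (0.1077/0.1219) to +3% (0.1015/0.0983), with no consistent direction.

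**The case against.** The strongest reply is that nothing is wrong with the model. The design has full rank, the likelihood is the same in any unit, and positive definiteness is preserved under rescaling in exact arithmetic. Failure is then a property of the algorithm. A Fisher-scoring REML fit to four simulated trials, with three and four random effects, converged in raw days in all eight fits within 4 to 6 iterations. Effect and SE agreed with t/336 to at least 10 decimals. In one of those trials the cubic covariance matrix was not positive definite in either unit, so there the data triggered the rule. All of this stands, and it limits the point to what can happen.

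Second, scaling and starting values belong in the program, which is blacked out. That also stands: the code may already rescale, and its absence from the public text is not an omission.

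Third, the interim model used day-based splines with a similar fallback and returned a usable sample-size estimate (SAP 8.3.3). The random part finally used is not stated, so this shows only that some fit succeeded.

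Fourth, SAP 14.2.3 plans a repeated-measures model with categorical visit and unstructured covariance, free of powers of time. It is a useful check on the covariance model, but as a sensitivity analysis it does not decide the primary test.

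A reader might infer that the primary model is singular, or that the analysis will collapse. Some simulated fits in days did give absurd standard errors, above 700,000 L. Those values reflect one optimiser's starting values and parametrisation, and the documents do not support that inference.

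**Conclusion.** The point holds as a risk that costs nothing to remove. SAP 14.1.4 and 14.1.5 define t in days, and the cubic cross-product then sits at the limit of double precision. In at least one general-purpose optimiser, the unit alone decided whether the cubic random model could be fitted. The drop rule and the AIC comparison can therefore be settled by the unit. Whether they would be in this trial depends on software settings that cannot be seen.

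The likely effect on the result is modest. The first step down, cubic to quadratic, made little difference without zero imputation. The 7 to 11% smaller SE arises only if the quadratic model fails as well and the linear one is used. Under the assumed 6% zero imputation the differences were larger but not consistent in direction. These sizes rest on assumed variances, few simulated trials and software other than the trial's own.

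**What to change.** In SAP 14.1.4, 14.1.5 and the program in 17.1, define t as study day/336 with the knot at 182/336, for both the spline and the random effects. Evaluate the Week 48 contrast at the scaled value, which is 337/336 for the nominal study day of 337 in Table 2. State that the AIC comparison and the drop rule apply only to converged fits in scaled time, and that a fit that has not converged does not enter the AIC comparison. If the program already rescales, one sentence saying so is enough.

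The cost is a few lines of text and code. The model, the estimand and the AIC ranking stay the same.

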### 14.2 Sensitivity Analyses for the Primary Endpoint

### 14.2.1 Missing data not at random (MNAR)

To investigate the impact of departures from MAR assumption, a MNAR approach will be evaluated using the LMM described for the primary analysis. After remapping of the visits as per section 9.4, FEV1 at specific visit will be imputed depending on the IE experienced by the patient.

In case of IEs as death or re-transplantation, FEV1 will be imputed as zero at each post-event nominal day as per section 9.4. Other IEs (see Table 5) will be addressed per treatment policy strategy, and FEV1 measurements collected after IE will be used in the analysis.

Residual missing data (or missing data due to discontinuation for consent withdrawal or patient lost to follow-up) will be imputed using fully conditional specification, a type of multiple imputation using chained equations, implemented with column under the FCS option. The imputation model will include baseline FEV1, age (as a continuous variable), region, use of azithromycin at randomization, and intermediate FEV1 up to week 48 as covariates. Two hundred data sets will be generated, and the random seed number will be 52082. In case of imputation, the associated nominal day of assessment will be considered as per section 9.4.

Only observed values from retrieved discontinued patients will be used to inform the MI regression model (this model will be defined as MI-RD). Retrieved discontinued patients are defined as patients who discontinue study treatment and decide to remain in the study by following the schedule of assessments and continuing to adhere to protocol requirements. If there are not enough retrieved patients for the convergence of MI-RD regression model, a reference-based MI will be adopted: imputation of values in the investigational arm will be done using the non-missing values from the control group (this approach will be referred as "Copy Reference"). This approach does not assume benefits for the investigational arm in case of discontinuation and limits a post-discontinuation clinical effect to that of SoC. The final decision on the use of the MI-RD vs Copy-Reference will be done at the time of the analysis and reported in the CSR.

Each of the 200 imputed datasets will be analyzed using the LMM (see primary analysis) including all observed and imputed data. Rubin's rule [2] will be used for combining results to draw inference.

The robustness of primary results will be evaluated by means of the adjusted difference between treatment groups in mean FEV1 change from baseline after 48 weeks. The p-value for the null hypothesis of no difference and a two-sided 95% confidence interval for the difference will be provided. The same comparison between treatment groups at all the other visits (2-8) will be presented.

The core excerpt of cole code for this sensitivity analysis is reported in section 17.2

The 200 imputed datasets will be used also for sensitivity analysis reported in section 14.2.4.

Final Version 5.0 Page 43 of 76

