#### 8.1.2 Treatment Definition

Treatment refers to add-on L-CsA to SoC therapy, as well as SoC therapy alone. Treatments periods are defined in section 15.2.2.

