### 14.2.2 Delta-Based Controlled Imputation (Tipping point)

A delta-based controlled imputation approach using the tipping point analysis will be performed as a sensitivity analysis of treatment superiority, if shown. Tipping point analysis will assess how departures from MAR assumption must be to overturn conclusions from the primary superiority analysis. Tipping point will be based on iterative application of MI.

In case of death or re-transplantation events, FEV1 will be imputed as zero at each nominal day post event.

In the first iteration, the missing FEV1 outcomes will be imputed separately for each treatment group, using the fully conditional specification. The imputation model will include baseline FEV1, age, region, use of azithromycin at randomization, and intermediate FEV1 up to week 48 as covariates. Two hundred data sets will be generated, and the random seed number will be 99823. Non-missing values from all patients will be used.

In successive iterations, to represent departures from MAR, values  $\Delta 1$  and  $\Delta 2$  will be added and subtracted to the imputed values for L-CsA plus SoC treatment and SOC treatment groups respectively.  $\Delta 1$  and  $\Delta 2$  will range from 0 to 100 mL (0.1 L) by 10 mL (0.01 L).

For each scenario (i.e., each combination of  $\Delta 1$  and  $\Delta 2$ ), the 200 delta-adjusted imputed datasets will be analyzed using the primary LMM including all observed and imputed data. Rubin's rule will be used for combining results to draw inference. The adjusted difference between treatment groups in mean FEV1 change from baseline after 48 weeks will be provided along with its p-value for the null hypothesis of no difference.

These results will show how extreme the departures from MAR must be to overturn the results of the primary analysis. Controlled imputation is always feasible, independent from the incidence of dropouts.

The core excerpt of code for this sensitivity analysis is reported in section 17.3.

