### 15.2.2 Exposure to Study treatment (SoC or SoC+L-CsA)

SoC therapy period starts at randomization date and stops at date of study completion or early termination. L-CsA treatment period starts at date of first dose of L-CsA and stops at the date of last dose administered.

Descriptive statistics for the duration of any study treatment (SoC or SoC+L-CsA) in days and weeks will be provided. Since the SoC will cover the entire study period post-randomization, the study treatment duration (SoC or SoC+L-CsA) will be calculated as the difference between the date of study completion/early termination and randomization plus 1.

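### As written, the MI-RD sensitivity analysis (SAP 14.2.1) fills missing SoC values and on-treatment L-CsA gaps essentially from patients who stopped L-CsA

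*SAP*

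**What the plan says.** SAP 14.2.1 sets deaths and re-transplantations to an FEV1 of zero. For the rest, "Residual missing data (or missing data due to discontinuation for consent withdrawal or patient lost to follow-up) will be imputed using fully conditional specification". That sentence is not limited to one arm.

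- **Donors:** "Only observed values from retrieved discontinued patients will be used to inform the MI regression model", and "Retrieved discontinued patients are defined as patients who discontinue study treatment and decide to remain in the study".
- **Covariates:** baseline FEV1, age, "region, use of azithromycin at randomization, and intermediate FEV 1 up to week 48 as covariates". Treatment is not listed. The tipping-point analysis in SAP 14.2.2 has much the same covariates but says that values are "imputed separately for each treatment group, using the fully conditional specification".
- **What counts as treatment:** "Treatment refers to add-on L-CsA to SoC therapy, as well as SoC therapy alone" (SAP 8.1.2). SAP 15.2.2 ends the SoC period at study completion or early termination, and computes duration accordingly: "Since the SoC will cover the entire study period post-randomization".
- **Fallback:** if there are too few retrieved patients for the model to converge, Copy Reference is used. It imputes the investigational arm from control-arm values; nothing is said about missing control-arm values. "The final decision on the use of the MI-RD vs Copy-Reference will be done at the time of the analysis".
- **Reuse:** the same 200 datasets feed the MMRM under MNAR in SAP 14.2.4.

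**The concern.** A retrieved-dropout model is meant to answer one question: what would FEV1 have been for patients who stopped L-CsA and then left, judged from those who stopped L-CsA and stayed? Section 14.2.1 applies it more widely.

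An SoC patient who withdraws consent has not stopped L-CsA, and an L-CsA patient with one rejected spirometry is still on the drug. Both would be imputed as if they had quit L-CsA. For the second group this also sits badly with SAP 14.1.1, which regards rejected spirometry as uninformative about outcome and compatible with MAR.

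The imputed SoC values would thus depend on how L-CsA quitters fare. Two analyses offered as separate support for the primary result, 14.2.1 and 14.2.4, would share the problem.

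**Working it through.** **1. Who can be a donor.** A donor has stopped study treatment and remains in the study. For SoC alone, 15.2.2 ends treatment when study participation ends. Under that definition the two conditions cannot both hold for an SoC patient, so the donors come from the L-CsA arm.

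**2. Who is imputed.** Three groups: SoC patients with missing values, L-CsA patients with intermittent gaps while on treatment, and L-CsA patients missing after stopping. Only the third matches the donors.

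**3. The plan's own figures.** SAP 8.2 assumes a 200 mL difference, SD 350 mL, one-sided 0.025 and at least 80% power with 50 per arm. The t-test power is 79.96% at 49 and 80.8% at 50 per arm, so the figure reproduces. With 169 randomized 1:1 (about 84 and 85), SE = 350 × √(1/84 + 1/85) = 53.8 mL. This serves as a yardstick and ignores covariates and missing data.

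**4. Shift relative to imputing SoC from SoC data.** Let m be the share of SoC Week 48 values imputed. Let g be how much lower L-CsA quitters are than SoC patients with missing data would be, given the covariates. The imputed SoC mean falls by m × g, so the difference moves by m × g. Both inputs are assumptions.

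| m | g = 50 mL | g = 100 mL | g = 200 mL |
|---|---|---|---|
| 5% | 2.5 | 5 | 10 |
| 10% | 5 | 10 | 20 |
| 20% | 10 | 20 | 40 |
| 33% | 16.5 | 33 | 66 |

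This is 2.5/53.8 = 0.05 SE to 66/53.8 = 1.23 SE. If g is negative the sign reverses. The 33% is an outer bound taken from the interim statement that completion stayed above 67% (SAP 8.3.3); it is not an SoC Week 48 figure.

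A simulation without covariates (85 per arm, 15 L-CsA quitters, m = 20%, g = 200 mL, no missing L-CsA values) agrees. The true difference was −35.3 mL; filling SoC from L-CsA quitters gave +5.1 mL and filling from SoC gave −36.5 mL. The gap of 41.6 mL compares with m × g = 40 mL.

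**5. Position relative to the MAR result.** The same model also fills the L-CsA arm. Set the SoC mean at 0, on-treatment L-CsA at +200 mL and quitters at −g, with missing shares mS (SoC) and mL (L-CsA), and ignore conditioning on earlier FEV1. MAR gives 200. As written, MI-RD gives 200 − mL(200 + g) + mS·g.

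- With mS = mL = 20%, this is 160 mL whatever g is. With SoC imputed from SoC data it would be 200 − 0.20 × 300 = 140 mL at g = 100, or 200 − 0.20 × 400 = 120 mL at g = 200.
- To exceed 200 requires mS·g > mL(200 + g): SoC missingness more than 3 times that in L-CsA at g = 100, or more than 2 times at g = 200.

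**6. Donor numbers.** With eight post-baseline visits, each conditional regression has about 12 coefficients: intercept, baseline FEV1, age, region, azithromycin and seven other visits. If 10–20% of 85 L-CsA patients stop and 50–100% of them are retrieved (assumed), there are 85 × 0.10 × 0.5 = 4 to 85 × 0.20 × 1.0 = 17 donors. In a simulated Bayesian regression with 12 coefficients and independent normal covariates, the median predictive SD is about 2.5 times the true residual SD with 14 donors and 1.6 times with 20. A model can therefore converge and still carry little information.

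**The case against.** **SoC discontinuation may be recordable.** A reader might infer that SoC patients cannot stop study treatment. No rule says so; it follows from an exposure convention. Protocol 10.3.1 encourages patients who stop treatment to continue regardless of arm, Protocol 15.2.2 tabulates early discontinuation of both study treatments, and SAP 10 reports treatment completion by group. A few SoC donors are therefore possible. They would still be pooled with L-CsA quitters, because no treatment term is stated.

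**The code is not visible.** A by-arm statement in SAP 17.2 cannot be excluded, and 14.2.2 shows that a covariate list without treatment can accompany by-arm imputation. This stands as a caveat. But if imputation is by arm, SoC has no donors under 15.2.2, so the text needs repair either way.

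**The check may still be conservative.** A reader might infer that it favours L-CsA over the primary result. Working step 5 shows otherwise: with similar missingness in both arms the estimate still falls below MAR. It is less conservative than it would be with SoC imputed from SoC data only if quitters do worse than SoC patients with missing data would.

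**The large shifts rest on assumptions.** The 67% is a floor for visit completion at a blinded interim analysis, pooled over arms. Week 48 is a mandatory on-site visit, and deaths and re-transplantations are not imputed by this model. A gap of 100–200 mL after conditioning on earlier FEV1 has no source in the documents. A few-millilitre shift is as compatible with the text as a large one.

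**Few donors work against the bias.** Inflated predictive variance widens intervals, and non-convergence would pass the analysis to Copy Reference, where SoC is not filled from quitters. That is fair, but Copy Reference then has no rule for missing SoC values.

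**Other checks exist.** By-arm tipping point, selection model, joint model and trimmed means are also planned, so the missing-data assessment does not rest on MI-RD alone.

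**Conclusion.** The point holds as a defect in a stated imputation rule. Read with 15.2.2, section 14.2.1 predicts missing SoC values and on-treatment L-CsA gaps essentially from L-CsA quitters, and its fallback leaves the control arm undefined.

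The resulting shift is about m × g, or 2.5–66 mL (0.05–1.23 SE) over the assumed ranges; its sign is unknown until the data are seen. This assumes no by-arm step in the unseen code and few or no recorded SoC discontinuations.

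The documents do not establish a bias toward L-CsA, nor an estimate above the primary one. Two sensitivity analyses are affected (14.2.1 and 14.2.4); the primary LMM and its type I error are not. The change should be made, but the primary inference does not depend on it.

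**What to change.** Amend SAP 14.2.1, the matching cells of Table 5 and the code in 17.2 as follows:

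1. Impute missing SoC values from SoC data under MAR.
2. Impute intermittent gaps in patients still on L-CsA within arm under MAR.
3. Use MI-RD only for L-CsA values missing after L-CsA discontinuation.
4. State how missing SoC values are handled under Copy Reference.
5. State whether an SoC patient can be recorded as discontinuing study treatment and, if so, how that patient is treated as a donor.
6. Set a minimum donor number, in addition to convergence, for choosing MI-RD over Copy Reference, and decide before unblinding. The blinded data review meeting, which already settles subgroup pooling before database lock (SAP 14.6), is a natural place.

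The cost is SAP text and programming, with no new data. There are more imputation steps, and the sensitivity result may be less favourable. The SoC arm would stay under MAR in this analysis; departures in SoC remain covered by the tipping-point analysis in 14.2.2.
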